5. REMOVAL OF SUBJECTS FROM STUDY TREATMENT OR ASSESSMENT

5.1. Discontinuation from Study Treatment

A subject's double-blind treatment may be discontinued for any of the following reasons:

- Worsening of disease (Note: If a subject discontinues double-blind treatment at any time starting with the Week 12 assessment, the subject may be eligible to enter the APD334-303 OLE [Section 5.1.1])
- Adverse event that in the judgement of the Investigator and/or Medical Monitor the subject should not continue study treatment
- Subject noncompliance with the protocol or study treatment that is considered significant by the Medical Monitor
- Investigator decision
- Withdrawal by subject or parent/guardian
- Lack of efficacy
- Lost to follow-up
- Study termination by Sponsor
- Other, non-adverse event

A subject's double-blind treatment must be discontinued for any of the following reasons:

- Decline in PFT values (FEV₁ and/or FVC) below 50% of the predicted values
- Confirmed diagnosis of clinically significant macular edema
- Confirmed diagnosis of active TB
- Subjects who have a cardiovascular treatment-related symptomatic event (eg, chest pain, dizziness, palpitations, lightheadedness, shortness of breath, or syncope) associated with reduction of the heart rate or associated with clinically relevant ECG changes at any time during the 4-hour monitoring period on Day 1 or Day 2 (as applicable) (Section 9.4.2.1)
- Subjects who have not met the discharge criteria on Day 1 after ≥ 4 hours of extended monitoring, or Day 2 by 4 hours post-dose (Table 4).
- Pregnancy (Section 9.10.9)
- Suspected drug induced liver injury as defined by the 2009 FDA Guidance for Industry (FDA 2009)
 - ALT or AST $> 8 \times$ ULN
 - ALT or AST $> 5 \times$ ULN for > 2 weeks
 - ALT or AST $> 3 \times$ ULN and (total bilirubin $> 2 \times$ ULN or international normalized ratio > 1.5)
 - ALT or AST $> 3 \times$ ULN with the appearance of fatigue, nausea, vomiting, right upper quadrant pain or tenderness, fever, rash, and/or eosinophilia ($> 5\%$)

Because transient fluctuations of ALT or AST are common, and progression to severe drug-induced liver injury or acute liver failure is uncommon, automatic discontinuation of study treatment upon finding a greater than $3 \times$ ULN elevation of ALT or AST may be unnecessary.

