5.2. Discontinuation from the Study

Subjects may be discontinued from the study at any time for any of the following reasons:

- Withdrawal by subject or parent/guardian
- Deviation/noncompliance with the study protocol that in the judgement of the Investigator and/or Medical Monitor the subject should not continue study treatment
- Study termination by Sponsor
- Lost to follow-up
- Death
- Other

A subject may withdraw from the study at any time for any reason without prejudice to their future medical care by the physician or at the institution. If a subject withdraws consent, no further evaluation should be performed, and no additional data should be collected. The Sponsor may retain and continue to use any data collected before such withdrawal of consent. The Investigator should make a reasonable attempt to document the specific reason why consent was withdrawn.

In the event that a subject fails to attend any follow-up visits, all reasonable efforts will be made to contact the subject to ensure that he/she is in satisfactory health. All contacts and contact attempts must be documented in the subject's file.

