10.4. Missing Data

Subjects with worsening of disease before Week 12 and subjects who meet the criteria for worsening disease after Week 12, as defined in Section 5.1.1, will be considered as having a treatment nonresponse outcome in the analysis of all endpoints, including the primary endpoint. In addition, subjects who initiate an agent not allowed in combination with the study treatment that can affect the efficacy of the study treatment, such as an immunosuppressant or corticosteroid, or who have an increase in dose over baseline levels for treatment of worsening disease symptoms will be considered nonresponders for binary responder-type endpoints thereafter or be handled by Per Protocol analysis.

Subjects discussed above will be considered as having a known outcome at the analysis timepoint (ie, a treatment failure outcome) and not as having missing data. Subjects who

discontinue the double-blind study for reasons other than worsening disease or adverse event related to UC will be considered as having missing data and will be handled in the primary and sensitivity analyses as follows.

A full description of the handling of missing data will be provided in the SAP.

Primary Method of Handling Missing Data

In the primary analysis of the primary endpoint and main analyses of all binary responder-type endpoints, all subjects with missing data, regardless of reason for missingness, will be considered as non-responders.

In the main analysis of continuous or score endpoints, such as changes from baseline in MMS subscores, biomarker measures, urgency NRS, abdominal pain NRS, and health-related quality of life measures, subjects with missing data will be analyzed with their observed data only, or a mixed-effect model with repeated measures. Detailed methods will be provided in the SAP.

Sensitivity Analyses for Missing Data

Sensitivity analyses will be performed under several alternative assumptions regarding missing data, ie, data missing intermittently, after discontinuation from the double-blind study for reasons other than worsening diseases, or after initiation of excluded medications.

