3.3. Changes to Analysis from Protocol

The primary analysis set for the efficacy endpoints is updated to the Full Analysis Set with MMS 5 to 9. Subgroup definition related to MMS is updated accordingly. The entire FAS will be used in supplementary analyses.

Definition of histologic improvement based on Geboes in Section 16 is updated from Geboes Index score < 3.1 to Geboes Index score ≤ 3.1.

The criterion of “Exclusion of other causes for loss of response unrelated to underlying UC (eg, infection)” is removed from the definition of “loss of response” in Section 16 since a more conservative approach is used.

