16.1.2. Missing Data Methods for Primary Efficacy Variables

Subjects who 1) discontinue the study for worsening of disease, lack of efficacy, or adverse event related to UC, 2) initiate a rescue medication for UC, 3) have an increase in dose over Baseline levels in their existing UC medication, or 4) have rescue medical procedure (eg, colectomy, ileostomy, or sigmoidectomy) during the study as confirmed after blinded review by clinical and medical team members before study unblinding will be considered to have a known (ie, nonmissing) outcome of nonresponse in the analysis of all efficacy endpoints at any subsequent timepoints, including the primary endpoint. The rescue medications will be identified by the Arena clinical team during blinded data review. Refer to [Appendix 7](#) for the definition of rescue therapies (medication and medical procedures). In scenarios 2 and 3 above, if a subject has an efficacy measurement collected after the initiation or dose increase from Baseline of UC medication, the observed data will be censored at the time of initiation or dose increase and they will be considered as having a nonresponse. Subjects in all 4 scenarios above may still be included in the respective Per Protocol Set, provided they do not violate other criteria for Per

Protocol Set. For example, they will be excluded from the respective Per Protocol Set if they initiate a prohibited medication before the Week 12 or Week 52 efficacy assessment that can affect efficacy of the study treatment and the indication is unrelated to UC.

Analysis visits will be mapped as per Section 6.4 before any missing data imputation method is applied.

Subjects with a missing efficacy outcome will be included in the primary analyses using the following missing data methods:

- Primary method: Single imputation as nonresponder
- Sensitivity analyses: Multiple imputation under missing at random (MAR), tipping point analysis, multiple imputation with Copy Reference (CR) under missing not at random (MNAR), and a hybrid imputation with multiple imputation to handle missing endoscopy data due to the COVID-19 pandemic impact and nonresponder imputation (NRI) for missing data not due to the COVID-19 pandemic impact. More details are provided in Section 16.1.4
- Supplementary analyses: mFAS analysis with data as observed, Per Protocol Set analysis (Week 12 Per Protocol Set for Week 12 endpoints and Week 52 Per Protocol Set for Week 52 endpoints)

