16.1.4.1. Multiple Imputation Under MAR

Any missing component scores of MMS at the planned assessments will be imputed using multiple imputation under MAR. MAR assumes the missing value is independent of unobserved outcomes given observed data (eg, subjects with missing RB subscores can be modeled based on subjects with observed RB subscores) (Rubin 1987).

The following steps will be implemented:

Step 1

Regardless of the arbitrary missing data pattern (ie, non-monotone or monotone), a fully conditional specification (FCS) method with predictive mean matching for continuous variables will be used to impute the missing data at all timepoints. The FCS method allows for separate conditional distributions for each imputed variable. The predictive mean matching approach creates a regression model using parameters sampled from the posterior distribution and then a predicted value for each missing value is computed. The missing value is replaced by randomly selecting an observation from a set of 'k' values that are the closest predicted values to the missing predicted value. Missing data imputation will be performed using the SAS PROC MI procedure. The number of imputations will be 40 and is based on a projected overall dropout rate of 50% and relative efficiency of ~ 99%. A separate imputation model will be used for each treatment group. The RB subscore, SF subscore, ES, PGA, stratification variables, a binary variable indicating if a subject is a prior UC treatment failure of oral 5-ASA only (ie, subject had an inadequate response, loss of response, or intolerance to previous treatment with oral 5-ASA and did not have an inadequate response, loss of response, or intolerance to any other previous UC medication), Geboes index score, and biomarker measurements (absolute lymphocyte count [ALC], fecal calprotectin [FCP], hs-CRP, log-transformed) at each planned visit will be included in the imputation models. Refer to [Appendix 3](#) for the order of variables and timepoints in the model.

Step 2

For each of the imputed datasets at Week 12 and Week 52, subjects will be classified as responder or nonresponder based on the criteria specified in Section 16. For each dataset, the proportion of responders will be calculated. For endpoints requiring MMS, MMS will be recomputed by summing the scores of ES, SF, and RB.

Step 3

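### SAP 16.1.2 ties fixed nonresponse to leaving the study rather than stopping treatment, so some treatment failures could be imputed as remitters in three sensitivity analyses, and it drops a Protocol 10.4 nonresponse rule without declaring the change

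*SAP*

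**What the plan says.** SAP 16.1.2 names four scenarios. Scenario 1 covers "Subjects who 1) discontinue the study for worsening of disease, lack of efficacy, or adverse event related to UC". Scenarios 2 to 4 are starting rescue medication for UC, raising the dose of existing UC medication above Baseline, and a rescue procedure. Subjects in any of the four "will be considered to have a known (ie, nonmissing) outcome of nonresponse in the analysis of all efficacy endpoints at any subsequent timepoints". Outcomes that are still missing count as nonresponse in the primary analysis. The same section then lists sensitivity analyses: multiple imputation under MAR, tipping point, Copy Reference, and a COVID-19 hybrid.

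Protocol 5.1 begins "A subject's double-blind treatment may be discontinued for any of the following reasons"; its list includes worsening of disease, adverse event and lack of efficacy. Protocol 5.2 begins "Subjects may be discontinued from the study at any time for any of the following reasons"; its list is withdrawal, deviation or noncompliance, sponsor termination, loss to follow-up, death and other. SAP Section 10 tabulates reasons off treatment and reasons off study separately.

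Protocol 10.4 states that "subjects who meet the criteria for worsening disease after Week 12, as defined in Section 5.1.1, will be considered as having a treatment nonresponse outcome", alongside subjects whose disease worsens before Week 12. It describes these subjects as having a known outcome, not missing data.

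In SAP 16.1.4.1, Step 1 imputes any missing MMS component score. In Step 2, "subjects will be classified as responder or nonresponder based on the criteria specified in Section 16".

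SAP 3.3 lists three changes from the protocol. The first is that "The primary analysis set for the efficacy endpoints is updated to the Full Analysis Set with MMS 5 to 9"; the other two concern histologic improvement and loss of response.

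**The concern.** A programmer applying scenario 1 has two reason fields to choose from, and the SAP's wording points to the one whose protocol list does not name these reasons. A subject who stops drug for worsening, starts no rescue, and is recorded as leaving the study for withdrawal or other would not meet scenario 1 on a literal reading. The estimand table does not help, because its three intercurrent events correspond to scenarios 2 to 4 only. The subject's Week 52 outcome is then missing and open to imputation, including imputation as a remitter.

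The imputation analyses are meant to show whether the coprimary result survives other assumptions about missing data. Subjects whose outcome the protocol treats as known should not be among those imputed.

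There is a separate gap in which nothing is missing. Under Protocol 10.4, a subject who meets the 5.1.1 criteria after Week 12, stays on blinded drug and is in observed remission at Week 52 is a nonresponder. Under the SAP the same subject is a responder unless one of scenarios 2 to 4 applies. Nonresponder imputation does not bridge that difference.

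**Working it through.** **The plan's own figures.** Exact power of Fisher's test with 280 and 140 subjects at two-sided 0.05 is 93.4% for 23.5% against 10.0% (Week 52) and 96.0% for 18.5% against 6.0% (Week 12), as stated. SAP 16.1.4.1 bases 40 imputations on a projected 50% overall dropout and about 99% relative efficiency: 1 / (1 + 0.5/40) = 0.988. The 50% is not divided by arm or by reason.

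**Primary analysis.** A failure coded as missing and a failure coded as known nonresponse both count as nonresponders. At planning rates the difference is 23.5 - 10.0 = 13.5 points under either reading, so the wording shifts it by 0.

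**COVID-19 hybrid (SAP 16.1.4.4).** Only endoscopy missing because of the pandemic is imputed; other missing data are nonresponse. A failure could be imputed only if the endoscopy were also missing for a COVID-19 reason, so the exposure is marginal.

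**MAR analysis, illustration.** Let p be the planning rate (all dropouts counted as nonresponse), d the dropout, and c = p/(1 - d) the completers' rate. Let f be the share of dropouts who are treatment failures, and k the imputed chance of remission relative to completers.

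- Study-based reading: rate = p + d·k·c
- Treatment-based reading: rate = p + d·(1 - f)·k·c

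Example with d = 0.5 in both arms, f = 0.5, k = 0.5. For etrasimod c = 0.47, giving 0.235 + 0.1175 = 35.2% (study-based) against 0.235 + 0.0588 = 29.4% (treatment-based). For placebo c = 0.20, giving 15.0% against 12.5%. The differences are 20.2 and 16.9 points.

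| Dropout, etrasimod / placebo | f | k | Difference, study-based | Difference, treatment-based |
|---|---|---|---|---|
| 50% / 50% | 0.25 | 0.25 | 16.9 | 16.0 |
| 50% / 50% | 0.5 | 0.5 | 20.2 | 16.9 |
| 50% / 50% | 0.75 | 1 | 27.0 | 16.9 |
| 42.5% / 65% | 0.25 | 0.25 | 13.2 | 13.3 |
| 42.5% / 65% | 0.5 | 0.5 | 12.9 | 13.2 |
| 42.5% / 65% | 0.75 | 1 | 12.3 | 13.2 |

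Both splits give 50% overall: (119 + 91)/420 = 0.5 for the second. With equal dropout, about 4 to 49 etrasimod and 1 to 11 placebo failures would be drawn as remitters.

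**Precision.** Take f = 2/3 and k = 1, and let a be the share of the arm not fixed as failures. The rate is a·c, with variance a²c(1 - c)/n(completers) + c²a(1 - a)/n. Completers in remission are 66 (etrasimod) and 14 (placebo).

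- 42.5% / 65%: z = 1.65 study-based, 2.71 treatment-based
- 45% / 60%: p = 0.011 study-based, 0.0015 treatment-based
- 50% / 50%: z = 4.26 study-based, 4.00 treatment-based

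The sign of the effect depends on the dropout split. Setting k = 1 is an upper bound, because the SAP's model conditions on earlier symptom, endoscopic and biomarker values, which would lower the imputed chance of remission for someone who worsened.

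**The other imputation analyses.** Copy Reference reuses Step 2 of 16.1.4.1. The tipping-point analysis has its own Step 2, which also classifies from scores. SAP Table 3 extends MAR and Copy Reference to endoscopic improvement, symptomatic remission and mucosal healing, and tipping point to the first two.

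**Can a subject meet 5.1.1 and stay?** Protocol 5.1.1 needs the investigator's opinion of no improvement or worsening, ES of at least 2, and symptoms at two timepoints 7 to 14 days apart. The Week 12 endoscopy can supply the ES, since it need not be repeated within 4 weeks. Entering the extension is optional. Such subjects are therefore possible, in number unknown.

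**The case against.** Much can be said for the SAP.

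- Protocol 10.4 itself speaks loosely of discontinuing the double-blind study when it separates worsening and UC-related adverse events from missing data. Scenario 1 follows that usage, so a treatment-based meaning was probably intended.
- The schedule has no continued efficacy visits after drug is stopped, so stopping treatment and leaving the study largely coincide.
- Protocol 5.2 has an open category of other, and the options on the End of Study form are not in the documents. A reader might infer that scenario 1 catches almost nobody; that cannot be established.
- A reader might also infer that the imputation has no safeguard for known failures. That goes too far: 16.1.2 declares scenarios 1 to 4 nonmissing and applies the imputation methods only to subjects with a missing outcome. The implementation detail in SAP Appendix 3 is redacted, so the absence of a flag cannot be inferred. What stands is that this safeguard is only as good as the trigger for scenario 1.
- A reader might infer that the coprimary tests or the gatekeeping are exposed through missing outcomes, or that a robust result would be made to look fragile. The first is excluded by nonresponder imputation; the second holds only for some dropout splits.
- The subject who meets 5.1.1 and stays is probably uncommon: Protocol Table 8 schedules no endoscopy between Weeks 12 and 52. Protocol 10.4 also defers the full description of missing data to the SAP. But it places these subjects outside missing data, so the deferral does not cover dropping the rule.

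**Conclusion.** The point holds in limited form. The trigger for scenario 1 does not match the protocol's lists of reasons, and read literally it leaves some treatment failures open to imputation as remitters in the MAR, tipping-point and Copy Reference analyses of the primary endpoints and of the key secondary endpoints that use them. It has no effect on the coprimary analysis of missing outcomes, and in substance none on the COVID-19 hybrid. In the MAR illustration the difference shifts by about +1 to +10 points with equal dropout, and by about -1 to 0 points with higher placebo dropout. Only the 50% overall dropout and the planning rates come from the documents; the arm split, the failure share and the imputed chance of remission are assumptions, so neither size nor direction can be claimed in advance.

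The departure from Protocol 10.4 is separate and does reach a coprimary endpoint, for subjects who meet 5.1.1 without stopping. Their number cannot be estimated from the documents. The defect is that a responder rule changed without being listed in SAP 3.3.

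**What to change.** 1. In SAP 16.1.2, scenario 1, replace the reference to discontinuing the study with *discontinue study treatment (reason off treatment per Protocol 5.1)*.
2. In Step 2 of 16.1.4.1 (which Copy Reference reuses) and Step 2 of 16.1.4.2, state that *subjects in scenarios 1 to 4 remain nonresponders in every imputed dataset from the event onward*.
3. Reconcile scenario 1 with Protocol 10.4. Otherwise list the change in SAP 3.3 and run the Protocol 10.4 rule once as a supplementary analysis of Week 52 remission, and of Week 12 remission for worsening before Week 12.

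All three should be settled before unblinding. The cost is wording, one flag in the imputation programs and at most one added supplementary analysis; no new data are needed. Remission rates in the imputation analyses will be lower in both arms than under the literal reading.

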16.1.3. Primary Analysis of Primary Efficacy Variables

The following hypotheses (H_{01} and H_{02}) for the coprimary endpoints will be tested:

H_{01} : The proportion of subjects achieving clinical remission at Week 12 is the same between etrasimod and placebo.

H_{11} : The proportion of subjects achieving clinical remission at Week 12 is different between etrasimod and placebo.

H_{02} : The proportion of subjects achieving clinical remission at Week 52 is the same between etrasimod and placebo.

H_{12} : The proportion of subjects achieving clinical remission at Week 52 is different between etrasimod and placebo.

Both hypotheses will be tested at the 2-sided α level, 0.05.

The primary efficacy analysis will be performed for the FAS with Baseline MMS 5 to 9. The Cochran-Mantel-Haenszel (CMH) test will be used, stratified by naïve to biologic or JAK inhibitor therapy at study entry (Yes or No), Baseline corticosteroid use (Yes or No), and Baseline disease activity (MMS: 4 to 6 or 7 to 9). Reported randomization stratum will be used in the model. Results will be expressed as the number and percentage of subjects in remission, difference in remission percentages and 95% CI and p-value, odds ratio and 95% CI. If there are no responders in both treatment groups in any stratum, the difference in remission percentages and associated inferences can still be made. However, the odds ratio and its CI may be calculated from the unstratified CMH.

16.1.4. Sensitivity Analysis of Primary Efficacy Variables

Four sensitivity analyses will be implemented to explore different types of missing data approaches: Multiple imputation under MAR, tipping point analysis, multiple imputation with CR under MNAR, and multiple imputation under MAR/NRI imputation hybrid. These sensitivity analyses will all use the FAS with Baseline MMS 5 to 9. There are 2 different types of missing data patterns: non-monotone and monotone. A subject with missing data at any post-Baseline visit, and a non-missing data point after that visit is said to have intermittent missing data (non-monotone). A subject with missing data at any post-Baseline visit and at all subsequent visits is said to have monotone missing data.

16.1.4.1. Multiple Imputation Under MAR

Any missing component scores of MMS at the planned assessments will be imputed using multiple imputation under MAR. MAR assumes the missing value is independent of unobserved outcomes given observed data (eg, subjects with missing RB subscores can be modeled based on subjects with observed RB subscores) (Rubin 1987).

The following steps will be implemented:

Step 1

Regardless of the arbitrary missing data pattern (ie, non-monotone or monotone), a fully conditional specification (FCS) method with predictive mean matching for continuous variables will be used to impute the missing data at all timepoints. The FCS method allows for separate conditional distributions for each imputed variable. The predictive mean matching approach creates a regression model using parameters sampled from the posterior distribution and then a predicted value for each missing value is computed. The missing value is replaced by randomly selecting an observation from a set of 'k' values that are the closest predicted values to the missing predicted value. Missing data imputation will be performed using the SAS PROC MI procedure. The number of imputations will be 40 and is based on a projected overall dropout rate of 50% and relative efficiency of ~ 99%. A separate imputation model will be used for each treatment group. The RB subscore, SF subscore, ES, PGA, stratification variables, a binary variable indicating if a subject is a prior UC treatment failure of oral 5-ASA only (ie, subject had an inadequate response, loss of response, or intolerance to previous treatment with oral 5-ASA and did not have an inadequate response, loss of response, or intolerance to any other previous UC medication), Geboes index score, and biomarker measurements (absolute lymphocyte count [ALC], fecal calprotectin [FCP], hs-CRP, log-transformed) at each planned visit will be included in the imputation models. Refer to [Appendix 3](#) for the order of variables and timepoints in the model.

Step 2

For each of the imputed datasets at Week 12 and Week 52, subjects will be classified as responder or nonresponder based on the criteria specified in Section 16. For each dataset, the proportion of responders will be calculated. For endpoints requiring MMS, MMS will be recomputed by summing the scores of ES, SF, and RB.

Step 3

The CMH test, stratified by naïve to biologic or JAK inhibitor therapy at study entry (Yes or No), Baseline corticosteroid use (Yes or No), and Baseline disease activity (MMS: 4 to 6 or 7 to 9) will be run for each of the 40 datasets to obtain 40 estimators of interest at Week 12 and Week 52.

Step 4

Use SAS PROC MIANALYZE to produce an overall pooled estimate (mean of 40 estimates) with its associated standard error (SE), CI and pooled p-value.

However, there could be certain adjustments due to unexpected data issues after unblinding treatment. All post-unblinding modifications to the multiple imputation model or approaches to address missing data will be described in the CSR.

